## 21) Common COVID-19 symptoms at baseline:

Common COVID-19 symptoms at baseline for each symptom will be considered as present if any of the corresponding FLU-PRO questionnaire items score 1 or higher at baseline.

Common COVID-19 symptoms	FLU-PRO questionnaire item
Stuffy or runny nose	Runny or dripping nose Congested or stuffy nose
Sore throat	Sore or painful throat
Shortness of breath (difficulty breathing)	Trouble breathing
Cough	Coughing
Low energy or tiredness	Weak or tired
Muscle or body aches	Body aches or pains
Headache	Headache
Chills or shivering	Chills or shivering
Feeling hot or feverish	Felt hot

Nausea	Felt nauseous (feeling like you wanted to throw-up)
Vomit	How many times did you vomit?
Diarrhea	How many times did you have diarrhea?
Loss of Smell	Loss of smell
Loss of taste	Loss of taste

22) SpO2 and respiration rate: -

Summary of SpO2 and respiration rate will include measurements obtained while participants are on room air. SpO2 and respiration rate obtained while participants are on supplemental oxygen will be listed.

23) Glucose:

Fasting is not required per protocol for collecting Glucose sample, mixed fasting Glucose and non-fasting Glucose results are presented in the dataset. Lab abnormality for Glucose will be summarized as follows:

- if fasting glucose is collected at baseline, max TE lab toxicity grade is selected for post-baseline fasting glucose, max post-baseline toxicity grade (i.e. not TE toxicity grade) is selected for the post-baseline glucose regardless of fasting status.
- if non-fasting glucose is collected at baseline, TE lab toxicity grade is selected for post-baseline non-fasting glucose, max post-baseline toxicity grade is selected for the post-baseline glucose regardless of fasting status.
- Max TE lab toxicity grade for fasting glucose and non-fasting glucose, max post-baseline toxicity grade for fasting glucose and non-fasting glucose will be summarized separately for Hyperglycemia, and Serum Glucose (regardless fasting or non-fasting status) for Hypoglycemia in the lab abnormality summary table.
- In the any TE lab toxicity section of the lab abnormality table, max post-baseline toxicity grade will be included.

24) SARs-CoV2 PCR data

- a) For numeric SARS-CoV2 summary (e.g, mean viral load, change from baseline etc.), “Inconclusive” SARs-CoV2 result is set to missing.
- b) For categorical SARS-CoV2 summary, 3 categories will be included if appropriate, i.e. Positive, Inconclusive, Negative.
  - i) Positive = any numeric result or “<LLOQ SARSCoV2 detected” - LLOQ could vary by sample type

- ii) Negative = “No SARS-CoV2 detected”
- iii) Inconclusive = “Inconclusive”
- c) For Negative SARS-CoV2 confirmation, “Inconclusive” SARS-CoV2 result will not be considered as missing thus a “Negative” followed by a “Inconclusive” is NOT confirmed.
- d) 2 negative results from the same day do not equal confirmation.
- e) if last PCR sample is negative for participants completed the study or for participant withdrawn early from the study, then one negative PCR of last sample is considered as confirmed negative.
- f) Categorical SARS-CoV2 and SARS-CoV2 negative summary will be separated out by sample type. There will be no combined Positive or negative category using 2 or more sample types.

25) SAS code for Cox model with Covariates

```
proc phreg;
class trt01p (ref="Placebo to match RDV") strat1 strat2 strat3;
model aval*cnsr(1) = trt01p strat1 strat2 strat3 /risklimits = wald;
ods output ParameterEstimates=Est1 ModelANOVA = pvout1;
run;
```

Hazard ratio is the hazardratio, 95% Cis are HRLowerCL and HRUpperCL where Parameter = “TRT01P” from EST1 dataset; P-value is ProbChiSq where Effect = “TRT01P” from pvout1 dataset.

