#### **2.1.1. DMC Analysis**

One external multidisciplinary DMC was planned to review the progress of the study and to perform interim reviews of the efficacy (futility assessment) and safety data. However, this DMC analysis was not performed due to the stop of study enrollment after 584 participants randomized and prior to reaching the planned DMC analysis schedule (ie, approximately 50% of the total 1264 planned participants have completed Day 28 assessment).

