**Table 3-4. Analysis Visit Windows for Hematology, Coagulation and Chemistry Laboratory Tests**

Nominal Visit	Nominal Study Day	Visit Window Study Day	
		Lower Limit	Upper Limit
Baseline	1	(none)	1 (Pre Dose)
Day 3	3	1 (Post Dose)	4
Day 7	7	5	9
Day 14	14	10	(none)

FLU-PRO Plus Questionnaire were to be collected daily from Day 1 through Day 14; therefore, windows are not assigned and results will be summarized for each Study Day.

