    - Symptoms scored as 2 or higher at baseline are scored as 0 or 1 at postbaseline, AND
    - Symptoms scored as 1 at baseline are scored as 0 at postbaseline, AND
    - for two consecutive days.
  - Time to alleviation of baseline COVID-19 symptoms is defined (in days) as:

First Date of the two consecutive dates achieving alleviation - First dose Date + 1

If a participant has not achieved symptom alleviation at last FLU-PRO Plus assessment or early discontinuation of study, the participant will be censored at last FLU-PRO Plus assessment date. Last assessment date is the last date when at least one of the baseline symptoms is assessed.
- Worsening after alleviation of baseline COVID-19 symptoms
  - The worsening after alleviation of baseline COVID-19 symptoms is defined as:
    - For a participant who has achieved alleviation of baseline COVID-19 symptoms
    - If any symptom scored as 2 or higher at baseline is scored as 2 or higher postbaseline after achieved alleviation, or
    - Any symptom scored as 1 at baseline are scored as 1 or higher postbaseline after achieved alleviation.
- Proportion of participants progressing to requiring oxygen supplementation by Day 28

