### 6.2.1. Analysis of Secondary Endpoints

The FAS will be the primary analysis set for secondary endpoints. The mFAS will be used for secondary endpoints of composite endpoint of COVID-19 related MAVs or death.

All-cause mortality by Day 28 will be compared between the 2 treatment groups using the Fisher exact test. If a participant prematurely discontinues from the study prior to Day 28 or the Death status is missing, the participant will not be included in the analysis.

The secondary endpoint of COVID-19 related hospitalization or all-cause death by Day 14, COVID-19 related MAVs or death by Day 28, and COVID-19 related MAVs or death by Day 14 will be analyzed using the same method as used for the primary endpoint, described in Section 6.1.3.

The proportion of participants hospitalized (COVID-19 related) by Day 28 will be estimated using the Kaplan-Meier method and compared between the 2 treatment groups using a log-rank test. Hazard ratio and two-sided 95% CI estimated using the Cox regression with baseline stratification factors as covariates will be provided.

Number and percentage of participants progressing to requiring oxygen supplementation by Day 28 will be summarized and compared between treatment groups using the Fisher Exact test. Participants discontinued from the study before progressing to requiring oxygen supplementation will be considered as not requiring oxygen supplementation.

The Kaplan-Meier product limit method will be used to estimate and log-rank test will be used to compare treatment groups for the time to alleviation of baseline COVID-19 symptoms. Hazard ratio and two-sided 95% CI estimated using the Cox regression with baseline stratification factors as covariates will be provided. Number and proportion of participants with worsening after alleviation of baseline COVID-19 symptoms will be summarized.

Time-weighted average change in SARS-CoV-2 viral load from baseline to Day 7 will be summarized by treatment groups and compared between treatment groups using an ANCOVA model with baseline viral load as covariate, the analysis will be based on the Virology Analysis Set.

CC1

[REDACTED]

[REDACTED]

[REDACTED]

[REDACTED]

[REDACTED]

[REDACTED]

[REDACTED]

[figure not shown]
[REDACTED]

[REDACTED]

CCI

CCI

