## **10. SOFTWARE**

SAS® Software Version 9.4. SAS Institute Inc., Cary, NC, USA.

Phoenix WinNonlin® 8.2. Pharsight Corporation, Princeton, NJ, USA.

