## 18) Symptom alleviation and time to baseline symptom alleviation

1. Baseline symptoms: Baseline symptoms are the symptoms collected prior to dosing and score  $\geq 1$ .
  - Item 1 to 34 of the FLUPRO are symptoms. Global assessments (last 6 items in the questionnaire) are not symptoms.
  - Each subject's baseline symptoms including number of symptoms likely are different.
  - For alleviation of baseline symptoms, only need to follow the symptoms presented ( $\geq 1$ ) at baseline
    - If a participant has 5 baseline symptoms, only the 5 symptoms will be followed to derive alleviation.
    - If a symptom (e.g. coughing) is not one of the baseline symptoms and has a score  $>1$  post baseline, the symptom will be not considered to derive the subject's baseline symptom alleviation.
    - If participant has not symptom  $\geq 1$  at baseline, alleviation status for the participant is missing for all visit.
    - Baseline symptoms  $\geq 1$ , symptoms from Day 2 and later are all missing, the alleviation status for the symptom is missing for all visits.
2. Alleviation of a symptom:
  - Symptom scored as 2 or higher at baseline are scored as 0 or 1 at postbaseline
  - Symptom scored as 1 at baseline are scored as 0 at postbaseline

- for two consecutive days - need to be confirmed with 2 visits
  - one missing day between two visits (that meets the alleviation definition) is allowed, but 2 or more days of missing is not considered reach alleviation
  - for Day 14 (or last assessment on Day x), if the symptom meets definition of alleviation, and day 13 (or Day x -1) also meets the definition of alleviation, then it is considered as confirmed. One missing day is allowed for the confirmation of Day 14 or last assessment, i.e if day 13 (or Day x-1 ) is missing and Day 12 (or Day x-2) meets the definition of alleviation, then it is considered as confirmed.

Examples:

Example	Day														Alleviation for a symptom on day	
	1	2	3	4	5	6	7	8	9	10	11	12	13	14		
1	2	2	2	1	1	1	0	0	0	0	0	0	0	0	4	baseline 2 or higher needs to be 1 or 0
2	2	2	2	0	1	1	0	0	0	0	0	0	0	0	4	baseline 2 or higher needs to be 1 or 0
3	2	2	2	0	2	1	1	0	0	0	0	0	0	0	6	day 4 is not confirmed
4	3	2	2	1	1	1	0	2	1	1	0	0	0	0	4	still on day 4 if worsen after confirmation
5	1	1	1	0	0	0	1	0	1	1	0	0	0	0	4	Worsening on day 7
6	1	1	1	1	0	0	0	0	0	0	0	0	0	0	5	baseline 1 needs to be 0
7	2	2	2	1	.	1	0	0	0	0	0	0	0	0	4	allow one missing

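### The SAP's only Cox code names no tie handling; if it is used for time to symptom alleviation, the default (Breslow) moves a non-null hazard ratio and its confidence interval slightly toward 1

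*SAP*

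**What the plan says.** Appendix 2, item 25 of the SAP carries a general heading for a Cox model with covariates and is the only Cox code given. Its model statement is "model aval*cnsr(1) = trt01p strat1 strat2 strat3 /risklimits = wald". The one option requests Wald limits. No section of the protocol or SAP says how tied event times are handled. SAP Section 10 names the software as "SAS® Software Version 9.4".

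For time to alleviation, SAP 6.2.1 plans two things. The between-group comparison is a log-rank test: "log-rank test will be used to compare treatment groups for the time to alleviation of baseline COVID-19 symptoms". The effect size comes from a Cox model: "Hazard ratio and two-sided 95% CI estimated using the Cox regression with baseline stratification factors as covariates will be provided".

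The event time is in whole days: "First Date of the two consecutive dates achieving alleviation - First dose Date + 1" (SAP 6.2). On the schedule, SAP 3.8.2 says "FLU-PRO Plus Questionnaire were to be collected daily from Day 1 through Day 14". Appendix 2, item 18 requires alleviation "for two consecutive days - need to be confirmed with 2 visits". SAP 3.5 treats every efficacy endpoint other than the primary as exploratory.

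**The concern.** When PROC PHREG is given no TIES option it uses Breslow's approximation. This is a property of the software, not something the SAP states. Breslow keeps every participant who has the event on a given day in the risk set for all of that day's events. With few events per day this hardly matters. With many, the arm with the higher event rate is over-represented in the denominators, and the estimated hazard ratio moves toward 1.

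Time to alleviation is where this could show: it is a daily-diary endpoint with few distinct event times. At stake are the reported hazard ratio and CI for the symptom objective, and whether that interval agrees with the log-rank p-value printed beside it.

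**Working it through.** **1. Inputs from the documents.** Day 1 is baseline, the diary ends on Day 14 and two days are needed for confirmation. The first day of alleviation can therefore fall on Days 2 to 13, which gives 13 − 2 + 1 = 12 possible event days. Enrolment ended early ("stop of study enrollment after 584 participants randomized"), so at most 584 participants contribute.

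**2. Assumptions.** The documents give neither an alleviation rate nor an expected hazard ratio for this endpoint. I take the placebo proportion alleviated by Day 13, F, as 30% to 85%, and a true hazard ratio (HR) of 1.3. Wider values follow in step 5.

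**3. The plan's own figure.** The plan states no figure for alleviation. The primary design figure reproduces:
- HR = ln(1 − 0.066)/ln(1 − 0.12) = 0.534.
- Events = 1264 × 0.95 × 0.093 = 111.7.
- Power = Φ(½ × √111.7 × |ln 0.534| − 1.96) = 91.2%, in line with the stated figure of more than 90%.

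**4. Hand check of the Breslow shift.** On one day with all events tied, setting the Breslow score to zero gives HR = p1/p0, the ratio of daily event proportions. The true HR is ln(1 − p1)/ln(1 − p0). With a constant hazard over 12 days, λ = −ln(1 − F)/12, p0 = 1 − exp(−λ) and p1 = 1 − exp(−1.3λ). The true log HR is ln 1.3 = 0.2624.

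| F (assumed) | p0 | p1 | Breslow HR = p1/p0 | log HR | Shrinkage by hand | Shrinkage in simulation |
|---|---|---|---|---|---|---|
| 30% | 0.0293 | 0.0379 | 1.294 | 0.2579 | 1.7% | 1.7% |
| 50% | 0.0561 | 0.0723 | 1.289 | 0.2538 | 3.3% | 3.2% |
| 70% | 0.0955 | 0.1223 | 1.281 | 0.2476 | 5.6% | 5.5% |
| 85% | 0.1462 | 0.1858 | 1.270 | 0.2394 | 8.8% | 8.5% |

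**5. Simulation with a wider range.** Proportional-hazards times were grouped to Days 2 to 13, with N = 584 and 200 trials per setting. For a true HR of 1.5:

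| F (assumed) | Events | Largest tie | Breslow HR | Efron HR | Ungrouped HR |
|---|---|---|---|---|---|
| 30% | 210 | 26 | 1.518 | 1.530 | 1.530 |
| 50% | 335 | 43 | 1.478 | 1.499 | 1.499 |
| 70% | 448 | 70 | 1.465 | 1.500 | 1.501 |
| 85% | 524 | 104 | 1.445 | 1.499 | 1.502 |
| 95% | 566 | 156 | 1.419 | 1.502 | 1.506 |

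Over HR 1.25 to 2.0 and F from 30% to 95%, the shrinkage of log HR runs from about 2% to 17%. At HR 1.5, the shift is 0.13 standard errors at 50% alleviation and 0.42 at 85%. With N = 300 the proportional shrinkage is the same and the shift in standard errors is smaller (0.09 and 0.31).

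**6. No effect.** At a true HR of 1 and F = 50%, Breslow and Efron both give 1.002.

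**7. Primary endpoint.** With 12% placebo events over 28 days and HR 0.534, the largest tie is about 5 at N = 584. Breslow gives 0.5456 and Efron 0.5450. At N = 1264 the values are 0.5361 and 0.5355.

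**8. Agreement with the log-rank test.** In 1000 trials per setting (292 per arm, HR 1.3, treatment-only Cox model), I counted trials where the log-rank test was significant but the Cox CI included 1. At F = 50% to 85% this happened in 3.2% to 4.4% of trials with Breslow and 0.2% to 0.5% with Efron. At F = 30% it was 1.4% against 0.4%.

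**The case against.** A reader might infer that the default weakens the significance test for symptom alleviation and costs power. The documents do not support that. SAP 6.2.1 compares the arms by log-rank and takes only the hazard ratio and CI from the Cox model, so no loss of power in a Cox Wald test carries over to the planned test.

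A reader might also assume that most participants alleviate. No rate is given, and the definition is strict. Every baseline symptom among 34 items must improve, a score of 1 must fall to 0, and the change must be confirmed. More than 25% of symptoms missing counts as not alleviated. The rate within 14 days could be low, and at 30% to 50% the shrinkage is only 2% to 3%. The questionnaire is collected only where available, so fewer than 584 may contribute, and the shift is then smaller relative to the wider interval.

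The link to this endpoint is inferred. Item 25 names no endpoint, and it extracts a Cox p-value, which fits the primary analysis better than 6.2.1. But it is the only Cox code, and its covariates are those 6.2.1 asks for.

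Finally, the bias runs toward no effect and falls on an exploratory endpoint. All of this stands and limits the point. It does not remove it: the hazard ratio is the reported effect size for this endpoint, and a conservative bias in an estimate is still a bias.

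**Conclusion.** The point holds, conditionally and at low priority. If item 25 is run as written for time to alleviation, the reported hazard ratio and CI are pulled toward 1 whenever treatment has an effect. For a true HR of 1.3 and assumed placebo alleviation of 30% to 85%, the log HR shrinks by about 2% to 8.5%, so the reported value would be about 1.29 to 1.27. Larger shifts need larger effects or near-universal alleviation.

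This rests on the PHREG default, on about 12 event days, on roughly proportional hazards, and on an alleviation rate the documents do not supply. The log-rank p-value does not change and no false positive can arise from this source. The primary hazard ratio moves only in the fourth decimal place. The practical consequence is a slightly understated effect size, and now and then a CI that includes 1 beside a significant log-rank test.

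**What to change.** Add ties=efron (or ties=exact) to the MODEL statement in Appendix 2, item 25, and name the method in SAP 6.2.1 where the Cox hazard ratio for time to alleviation is described. The same code can then serve every Cox analysis, since the primary result is essentially the same either way. Make the change before the blind is broken, so that tie handling is not chosen after seeing results. If the SAP is already final, record it in the clinical study report, as SAP Section 1 provides. The cost is one code option and one sentence; no new data are needed, and neither the design nor the planned tests change.
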